This project will use a factorial experiment (Table 1) to test the main and interactive effects of 3 centralized, healthcare system-delivered intervention components designed to enhance use of either standard care or more intensive, evidence-based cessation treatments. Standard care comprises referral to a toll-free state tobacco quitline offering a starter kit of nicotine replacement therapy and a single proactive counseling call to all Wisconsin residents who smoke, and/or referral to a primary care provider for brief smoking cessation advice/counseling and medication. More intensive treatment comprises varenicline or combination nicotine replacement therapy (NRT) with three counseling calls. Access to more intensive treatment (among those who meet medical eligibility criteria for varenicline and/or combination NRT use) will be randomly assigned on a

Table 1. Study Design: 2x2x2x2 Factorial Screening Experiment

Participants: Adult daily smokers in primary care not willing to quit within the next 30 days 
 Experimental sample: Target sample size of 300 patients eligible to use C-NRT* and/or varenicline and willing to be randomized to 4th factor below ~416 patients eligible for neither C-NRT nor varenicline
Intervention Components: 
 Incentives (\$40 for each 1st counseling call in up to 4 rounds of treatment over 2 years, maximum \$160) vs. none Semi-annual automated, tailored mailed and electronic-health-record outreach promoting treatment vs. generic letters Semi-annual proactive telephone-delivered care management (outreach and motivational intervention) vs. none Access to intensive care (12 weeks of either C-NRT or varenicline, with 3 counseling calls) vs. standard care (counseling and medication from quitline and/or patient's primary care provider)
Outcome: Any use of smoking cessation treatment in the 1 st year of enrollment and over 2 years of enrollment (primary) and abstinence (secondary)
Final Product: Optimized reach interventions to promote smoking cessation treatment utilization that will be evaluated in an RCT

*C-NRT= Combination Nicotine Replacement Therapy (patch + mini-lozenge)

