Aim 1. To develop an optimized package of health system interventions to promote smoking cessation treatment reach among patients not initially willing to quit, logistic regression analyses will be conducted with binary treatment initiation over 1 year of study enrollment as the primary outcome, in the primary sample randomized on all 4 experimental factors. Effect size estimates will be generated and all main and all 2-way, 3-way, and 4-way interactive effects will be tested as predictors in the logistic regression model. In addition, the magnitude of the difference in treatment initiation rates between the most promising intervention conditions and the cell in which all the intervention components are off will be used to generate an upper limit estimate of optimized reach intervention package effects. Exploratory analyses will be conducted adjusted for covariates known to be predictive of treatment use. Exploratory sensitivity analyses will be conducted to estimate intervention component effects across a range of assumptions regarding missing outcome data. We anticipate that 25% of follow-up data will be missing and will examine the robustness of results across intent-to-treat and less stringent assumptions regarding missingness (i.e., that 90%, 80%, or 70% of missing cases are smoking) in sensitivity analyses. We may also use multiple imputation and examine the consistency of results across multiply imputed datasets and those imputed using the simple methods already described. This analysis will use data collected via UW-CTRI staff during follow-up telephone interviews supplemented by data regarding smoking cessation attempts and treatment utilization extracted from the EHR and the WTQL.

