Aim 2. To assess the cumulative main and interactive effects of each intervention component on binary treatment initiation over 2 years of study enrollment, logistic regressions predicting any treatment initiation (defined as completing a first counseling session, the primary outcome at a more distal endpoint) will address this aim, first in the ~240-300 patients (max 300) eligible for intensive treatment to examine all 4 intervention components, and then, separately, in the ~30-60 (max 60) participants who do not meet criteria for access to intensive treatment. As in the analyses for Aim 1, effect coding will be used to ensure the independence of the main and interactive effects in this balanced design, exploratory analyses will be conducted with adjustment for covariates, and exploratory sensitivity analyses will examine the robustness of results across a range of missing data assumptions.

In addition to the binary logistic regression described above, exploratory logistic regression models will estimate intervention component main and interactive effects on treatment completion (all 3 counseling sessions and medication initiation) among those randomly assigned to have access to intensive treatment with C-NRT or varenicline and counseling. This exploratory analysis will quantify the effects of the informational/motivational intervention components on the dose of evidence-based treatment received by participants over 2 years. Effect coding, covariate adjustment, and sensitivity analyses will be used, as described above. Exploratory descriptive analyses of the frequency and temporal patterns of treatment use will also be conducted (e.g., to explore whether C-NRT use tends to follow varenicline more often than the reverse, to see whether C-NRT is more likely to be repeated than varenicline use). As for Aim 1, this analysis will use data collected via UW-CTRI staff during follow-up telephone interviews supplemented by data regarding smoking cessation attempts and treatment utilization extracted from the EHR.

Secondary Aim 1. Although the primary outcome in this study is treatment reach, the ultimate objective of this project is to help more smokers stop smoking. A key secondary binary logistic regression analysis in this project will estimate reach-focused intervention component effects on end-of-study 7-day point-prevalence abstinence confirmed by CO testing, and, if CO is elevated,

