Supplemental Models. Exploratory GEE models may examine intervention component effects on the pattern of treatment initiation and abstinence across the 4 semi-annual follow-up waves. Additional, exploratory latent class analyses may examine patterns of engagement and abstinence in 6-month epochs over 2 years, conditional on intervention components and combinations. These supplemental analyses will be exploratory and hypothesis generating. Their results may facilitate interpretation of interaction effects in the primary analyses and inform refinement of optimized combinations of reach-focused system interventions.

Covariates. All models described above will be conducted and reported with and without adjustment for healthcare system or clinic and factors known to be associated with treatment engagement (e.g., sex, age, medical comorbidities related to smoking, healthcare utilization⁷³⁻⁷⁷). Covariates will be removed from final adjusted models if not significantly related to the dependent variable to enhance model parsimony.

Power and Sample Size

The target sample size for participants eligible for randomization to intensive treatment access ($N=1664$) was selected based on estimates of the flow of patients through clinics in a 9-month period and the number needed to detect at least an 8% increment in both treatment reach (defined here as initiation or completion of treatment) and 2-year abstinence rates, as we consider 8% to be a clinically meaningful increment in both reach and abstinence. Power estimates for main effects of each intervention component across a range of possible base rates in treatment use (from 5 to 65%) and abstinence (from 5 to 30%) exceed .9 (at alpha .05) with a sample of 1664 participants. Power to detect simple main effects (i.e., to interpret interactions) exceeds .7 for all but one combination of base rates and effect sizes at $N=1664$.

Power will be lower in the sample of smokers who do not meet all eligibility criteria for randomization to intensive treatment access (we estimate this to be roughly 416 participants, but may be as high as 800 participants), but this sample will be sufficiently large to generate

upper-bound estimates of effect sizes for intervention component, component-by-component interaction, and mediator and moderator effects.

July 2022 update to sample size based on recruitment challenges

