Initially, the sample size was N=1664 to provide adequate power to detect hypothesized effects (8% increments in treatment reach, or initiation of assisted quit attempts, and 8% increments in abstinence 2-years after enrollment). Given difficulties in recruitment using the current model, we recognize that this sample size is not feasible to achieve during the study period. As such, we have now revised our goals for this study and now propose a sample of 240-300 participants. This will ensure that at least 15 participants are in each cell of the experimental design, sufficient to yield stable estimates of effect sizes in this factorial design. Although this sample size will not provide adequate power to test hypothesized effects, it will be sufficient to generate effect size estimates and ranges, and to identify interventions and intervention combinations with promising effect sizes for future study.

H. Human Subjects Protections and Data Sharing

Describe any potential direct benefits to subjects. If there are no direct benefits, state this.

Every participant in the study will be given information about ways to access at least 1 evidence-based treatment to help them stop smoking and will be given access to that treatment at no direct personal cost (apart from possible telephone charges for telephone-delivered care such as cessation counseling and care management). Although smokers could access this care outside of the study, we know that only about 1-2% of smokers use a quit line and only about 5% use both medication and counseling. As such, the proposed study will offer all participants the benefit of information about treatment options and a low-barrier method of initiating treatment (i.e., by phone).

Describe the potential benefits of this research to society.

The proposed research also has the potential to benefit other smokers by identifying highly effective health system reach interventions that expand the reach of existing lower- and higher-intensity treatments and are feasible, cost-effective, and potentially sustainable in primary care settings. This work has the potential to accelerate the translation of clinical research on smoking interventions into healthcare practice and thereby reduce morbidity and mortality associated with smoking.

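### Aim 1's saturated logistic model has no fallback for cells without treatment initiators, and after the cut to 15–19 patients per cell such cells are likely if reach is low

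*Combined protocol and SAP*

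**What the plan says.** Under Analysis Plan, Aim 1, 1-year treatment initiation (yes/no) is analysed by logistic regression in patients randomized on all four factors, and "all main and all 2-way, 3-way, and 4-way interactive effects will be tested as predictors in the logistic regression model". Aim 2 applies the same kind of model at 2 years, states that effect coding is used for both aims, and describes initiation as "defined as completing a first counseling session".

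The July 2022 update to the sample size reduces N from 1664 to 240–300, with at least 15 patients per cell; Table 1 gives a "Target sample size of 300 patients eligible to use C-NRT* and/or varenicline". The update concedes that power is inadequate. It justifies the smaller trial as "sufficient to yield stable estimates of effect sizes in this factorial design" and "sufficient to generate effect size estimates and ranges, and to identify interventions and intervention combinations with promising effect sizes for future study".

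Power and Sample Size considers base rates of treatment use from 5% to 65% and a target increment of 8 percentage points. No expected 1-year reach is stated.

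The one Aim 1 quantity not on the log-odds scale is "the difference in treatment initiation rates between the most promising intervention conditions and the cell in which all the intervention components are off", intended as an upper limit for the package effect. The sensitivity analyses deal with covariates and missing outcomes. Nothing is said about empty cells, separation, penalised or exact estimation, or dropping interaction terms.

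**The concern.** A saturated logistic model reproduces the 16 cell proportions exactly. If a cell has no initiators, its fitted log-odds is minus infinity. Under effect coding that cell enters every coefficient, so the main effects are lost along with the four-way interaction. At 104 patients per cell this was a remote risk. At 15–19 it depends on how many patients take up treatment, and every participant starts out not ready to quit within 30 days.

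Once power has been conceded, estimating effects for components and their combinations is the reason that remains for running the trial. If the specified model returns no finite log-odds estimates, the analyst must choose a repair after seeing the data: drop terms, merge cells, add constants or penalise. That choice could change which components look promising enough for the optimized package.

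**Working it through.** **Inputs.** There are 16 cells (Table 3). N is 240–300 now and was 1664 (July 2022 update). Base rates are 5–65% and the increment is 8 points (Power and Sample Size). Anticipated missing follow-up is 25% (Aim 1). Equal allocation is assumed.

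**The plan's own figure.** 240/16 = 15, which agrees with the stated minimum per cell. 300/16 = 18.75, taken as 12 cells of 19 and 4 of 18. 1664/16 = 104.

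**Why one empty cell is enough.** There are 4 + 6 + 4 + 1 = 15 effects plus an intercept, so 16 parameters for 16 cells. With −1/+1 coding, X′X = 16I, and each coefficient is (1/16) Σ ±logit(cell). Enumerating all sets of empty cells gives:
- one empty cell: all 15 effects diverge;
- two: 7 diverge and 8 are indeterminate (infinity minus infinity);
- three: 3 diverge and 12 are indeterminate.

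An ordinary fit with one empty cell confirmed this: the coefficients kept drifting and the standard errors rose from 0.3 at 5 iterations to about 5747 at 25.

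**Probability of at least one empty cell.** P = 1 − ∏[1 − (1 − p)^n] over the 16 cells. At p = 15%:
- N=240: 0.85^15 = 0.0874, so P = 1 − 0.9126^16 = 0.77.
- N=300: 0.85^19 = 0.0456 and 0.85^18 = 0.0536, so P = 1 − 0.9544^12 × 0.9464^4 = 0.54.

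| Common reach | N=240 | N=300 | N=1664 |
|---|---|---|---|
| 5% | ~100% | ~100% | 7% |
| 10% | 97.5% | 91% | 0.03% |
| 15% | 77% | 54% | ~0 |
| 20% | 44% | 22% | ~0 |
| 25% | 19% | 7% | ~0 |
| 30% | 7% | 2% | ~0 |
| 40% | <1% | <1% | ~0 |

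P reaches 50% at a reach of 19.0% (N=240) or 15.5% (N=300), against 3.0% at N=1664. It falls to 10% at 28.5% or 23.5%.

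**Unequal reach** (N=240 / N=300):

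| All-off rate | One component +8 points | All four +8 points |
|---|---|---|
| 5% | ~100% / 99% | 74% / 58% |
| 10% | 90% / 75% | 40% / 24% |
| 15% | 59% / 36% | 18% / 8% |
| 20% | 29% / 13% | 7% / 3% |

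**Missing data.** With 25% missing, the 50% points rise to about 24% / 20% for complete cases, or to a true reach of about 25% / 21% if missing counts as not initiated.

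**How the alternatives behave.** In the saturated model, Firth estimation equals adding 0.5 to events and non-events in each cell, so expected shrinkage is exact. In simulation (20,000 trials per scenario: null at 5–20%, and one or four components +8 points from 5% and 10%), Firth gave finite estimates in every trial, and its main-effect profile intervals covered 95.3–99.7%. The marginal risk difference compares 120–150 patients per level. Its mean was within 0.1 point of the truth, its Newcombe interval covered 95.0–96.4%, and its average half-width was 5.3–10.9 points.

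**The case against.** **The scale.** The strongest reply is that the failure lies on a scale the plan never makes its target. Aim 1 promises effect sizes without naming log-odds, the target is an 8-point increment, and the package estimate is a rate difference. All of these survive an empty cell. This stands in part, and the loss should not be described as wider than the log-odds effects with their Wald tests and intervals. But the only rate difference actually planned compares the best conditions with the all-off cell. It gives no component or interaction effect, and logistic regression is the only method Aim 1 names for those. The GEE and regression-tree analyses elsewhere are optional and are not offered as fallbacks.

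**Reach.** Reach may be high enough to avoid the problem. Every participant receives outreach letters, a registry-based campaign cited under Automated Tailored Outreach had a 30% response, and the wider definition of use in Table 1 would raise the rate. This also stands: whether this trial will be affected cannot be known from the documents. If all four components add 8 points, the 50% point corresponds to an all-off rate of only about 8% (N=240) or 6% (N=300). However, for a given average reach, equal cells are the most favourable case, and missing data raise the thresholds.

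**A simpler fallback.** Dropping higher-order terms is an alternative. In a check of 1,500 trials per setting with equal reach, a model with main effects and two-way terms was non-finite in about 5% (N=240) or 1% (N=300) of trials at 10% reach, but in 58% or 40% at 5%. Main effects alone failed in under 2% even at 5%. Such a rule would be workable if stated in advance; the plan states none.

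**Consequence.** This is a screening experiment with conceded low power, so no confirmatory test is at risk. That limits the severity. It does not remove the need for a defined estimator in a study that now exists to estimate.

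**Conclusion.** The concern holds and should be fixed. With the model as written, an empty cell is more likely than not below about 19.0% reach at N=240 or 15.5% at N=300, assuming equal reach, equal allocation and full follow-up. Both points lie in the lowest quarter of the plan's 5–65% range. The arithmetic is firm; whether this trial falls in that region is unknown, and at 30% reach the problem nearly disappears. At N=1664 the risk was negligible except near 5% reach, so the gap comes from cutting the sample without changing the analysis. The statement that the sample is "sufficient to yield stable estimates of effect sizes in this factorial design" does not hold at low reach for unpenalised log-odds effects.

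**What to change.** In Aims 1 and 2, pre-specify:

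1. Each component's marginal risk difference with a Newcombe 95% interval as the lead effect size, on the same scale as the 8-point target.
2. Firth-penalised logistic regression for the same effect-coded terms, with profile penalised-likelihood intervals and tests, and with interaction estimates labelled exploratory.

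In the July 2022 update, qualify the claim of stable estimates accordingly.

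The change is to wording only, with no new data or patients. Firth has a price that should be disclosed (N=240 / N=300):

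- **Main-effect shrinkage toward zero:** with one component +8 points, 22.5% / 16.0% from a 5% base and 7.3% / 3.8% from 10%. With all four +8 points, 6.6% / 4.2% and 1.5% / 0.6%.
- **Interaction shrinkage:** with all four +8 points from a 5% base, the 2-, 3- and 4-way terms lose 31/53/73% at N=240 and 21/40/59% at N=300. From a 10% base the losses are 13/28/50% and 6/16/32%. The true interactions here are small: the 2-way terms are −0.05 and −0.03, against an estimate SD of 0.14–0.17.
- **Conservatism:** main-effect null rejection is 0.3% / 0.7% at 5% reach and 2.1% / 2.8% at 10%.

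With one component +8 points from a 5% base, Firth detects the effect in 36% / 51% of trials and the risk difference in 58% / 69%. That is why the risk difference should lead. Firth makes interaction estimates finite; it does not make them precise.

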This project will use an efficient 2x2x2x2 factorial design (Table 1) to identify reach-focused intervention components that either singly, or in combination, increase patient use of evidence-based smoking cessation treatment over 2 years of availability and, by extending treatment reach, reduce smoking prevalence 2 years after enrollment. All adult patients who smoke daily, but who are **not willing to enter smoking cessation treatment** at the time of enrollment (the vast majority of smokers⁴⁰) will be eligible to participate, with no obligation to quit smoking or use treatment. Participants (N=240-300) will be recruited in 4-12 primary care clinics in 2 healthcare systems by system staff using an opt-out strategy⁴¹ to maximize inclusion and enhance dissemination and the generalizability of results. (Roughly 60 additional patients who do not meet eligibility criteria for intensive counseling and medication with either combination NRT or varenicline will be included in the study but will not be part of the experimental sample.)

This will be the first factorial experiment in healthcare settings to test interventions designed to extend the reach of varied smoking cessation treatments in primary care patients who are not initially willing to make an aided quit attempt (see Table 1). This rigorous and efficient factorial design will address the following aims:

Primary Aims

1. To **create an optimized reach intervention package** by identifying intervention components that increase cessation treatment reach especially well, at low cost, at 1-year follow-up.
2. To estimate the **main and interactive effects** of the intervention components on cumulative treatment **reach over 2 years** of treatment access.

Secondary Aims

1. To estimate the main and interactive effects of intervention components on **abstinence** at 2-year follow-up.
2. To identify the degree to which intervention component effects on 2-year abstinence are **mediated by increases in cessation treatment reach**.
3. To assess the **cost-effectiveness** of intervention components in promoting reach and abstinence.
4. To identify patient and clinic **moderators** of intervention component effects on reach and abstinence.

III. METHODS

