Following randomization, healthcare system Tobacco Care Managers will describe the stop-smoking treatments available to participants over the next 2 years (as determined by eligibility for and randomized access to intensive treatment condition), and will give instructions about how to contact him/her when ready to initiate smoking treatment. Those randomized to the incentive conditions will be told that they will receive \$40 for completing a first smoking cessation counseling session if/when they decide to enter treatment (they can earn the incentive up to twice per year [four times maximum] over the 2-year study). The Tobacco Care Manager

Table 3. Conditions (cells) to which participants will be randomized*

Cell	Incentives for treatment initiation	Automated tailored letters 2x/year	Care Manager Outreach 2x/year	Access to Intensive Treatment
1.	Off	Generic	Off	Off
2.	On	Generic	Off	Off
3.	Off	Tailored	Off	Off
4.	On	Tailored	Off	Off
5.	Off	Generic	On	Off
6.	On	Generic	On	Off
7.	Off	Tailored	On	Off
8.	On	Tailored	On	Off
9.	Off	Generic	Off	On
10.	On	Generic	Off	On
11.	Off	Tailored	Off	On
12.	On	Tailored	Off	On
13.	Off	Generic	On	On
14.	On	Generic	On	On
15.	Off	Tailored	On	On
16.	On	Tailored	On	On

* Those meeting initial criteria for access to intensive treatment will be randomized to all 16 cells; those ineligible for intensive treatment will be randomized to only the first 8 cells.

will also remind the participant that the study team will be reaching out in 6 months to conduct a brief follow-up assessment interview and the healthcare system will reach out again via letter in 6 months to provide information about resources and support available to quit smoking. If the person is randomized to a care management condition, the Care Manager will also schedule a 15-minute phone call for a motivational intervention within the next 2 weeks (with the option to complete the call immediately, if the participant is interested in doing so).

E. Welcome mailing

Following the enrollment call, study staff will mail enrollees a welcome package containing the following (samples of which are uploaded with the application):

1. A study Welcome Letter and a Treatment Offer Letter with information about:
 - a. Available smoking cessation treatments and evidence of their effectiveness. In the tailored letter condition, this information will be tailored and personalized.
 - b. Instructions about ways to contact the Care Manager to request treatment.

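### The promised minimum of 15 per cell is only the average at N=240, and Aim 1's upper-limit package effect is a selected estimate with no selection rule, interval or optimism correction

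*Combined protocol and SAP*

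**What the plan says.** **Cell size.** The July 2022 update (Power and Sample Size) cuts the experimental sample from 1664 to 240–300 and states: "This will ensure that at least 15 participants are in each cell of the experimental design, sufficient to yield stable estimates of effect sizes". It concedes that power is inadequate for the hypothesised effects, but says of the new size that "it will be sufficient to generate effect size estimates and ranges". Table 1 gives 300 as the target. Section D blocks randomization by clinic, gender and eligibility for the fourth factor, without a block size. Goals/Aims gives 4–12 clinics. The Data Safety and Monitoring Plan has allocation rates reviewed by clinic, sex and eligibility.

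**Package effect.** Analysis Plan, Aim 1 fits a logistic model for one-year treatment initiation with every main effect and every interaction up to the 4-way. A further step takes the "difference in treatment initiation rates between the most promising intervention conditions and the cell in which all the intervention components are off". On the purpose of this contrast, the same sentence says that it "will be used to generate an upper limit estimate of optimized reach intervention package effects". Goals/Aims describes the task as "identifying intervention components that increase cessation treatment reach especially well, at low cost, at 1-year follow-up", which points to choosing components. Table 3 is titled "Conditions (cells) to which participants will be randomized", so conditions can also be read as cells. Neither section says how the most promising are identified, attaches an interval to this contrast, or adjusts for choosing and estimating on the same data. Aim 1 also notes: "We anticipate that 25% of follow-up data will be missing".

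**The concern.** After the revision, the study's stated job is to find interventions and combinations that look promising for further study, and Table 1 sends the resulting package to an RCT. Two statements carry that job: that every cell is large enough for stable estimates, and that the package contrast gives an upper limit.

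The first turns an average into a guarantee. The second labels a selected point estimate as though it were a bound. Without a rule and an interval, a reader planning the RCT cannot tell how much of the reported package effect comes from selection. That share grew when the mean cell size fell from 1664/16 = 104 to 15–19.

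**Working it through.** **1. The plan's figure.** 240/16 = 15.0 and 300/16 = 18.75. The 15 reproduces, but as the mean at the lower end of the range.

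**2. Is 15 a minimum?** Inputs: 16 cells; 4–12 clinics × 2 genders (assumed) = 8–24 strata, all within the eligible sample. Block size is not stated, so 16 and 32 are assumed. A hand case: 8 clinics give 16 strata, and 240/16 = 15 per stratum. With blocks of 16, each stratum leaves one cell empty. All cells reach 15 only if each cell is left empty exactly once: 16!/16^16 ≈ 0.000001. Simulating strata whose sizes vary at random around equal or unequal shares:

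| | N=240 | N=300 |
|---|---|---|
| Cells below 15, average | about 5–7 of 16 | – |
| Smallest cell, average | about 9.6–13 | – |
| All cells ≥15, blocks of 16 | no draw | about 73–100% |
| All cells ≥15, blocks of 32 | no draw | about 15–99% |

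If the anticipated 25% of follow-up were missing from every cell, mean observed size would be 15 × 0.75 = 11.25 to 18.75 × 0.75 = 14.06, although quitline and EHR data may fill some of this.

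**3. Precision.** 95% half-width = 1.96·√(k·p(1−p)/N), with k = 4 (main effect), 16 (2-way, difference of differences) and 32 (cell versus cell). At p = 0.20, N=240, main effect: 1.96·√(4×0.16/240) = 10.1 points.

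| Half-width at 20% reach, points | N=240 | N=300 |
|---|---|---|
| Main effect | 10 | 9 |
| 2-way | 20 | 18 |
| Cell versus cell | 29 | 26 |

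**4. Optimism when no component works.** Base rates are 5–65%, the range in Power and Sample Size. For one main effect, SE = 2·√(p(1−p)/N). Keeping every positive component and summing gives an expected 4 × 0.399 × SE. At N=240 this is 4 × 0.399 × 2.81 = 4.5 points (p = 5%) and 4 × 0.399 × 6.45 = 10.3 (p = 50%). Keeping components only at z>1.96 gives 4 × 0.058 × SE, about 0.7 to 1.5 at N=240; 0.975⁴ ≈ 90% of null trials keep nothing. Simulated averages:

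| Selection rule | 15–19 per cell | 104 per cell |
|---|---|---|
| z>1.96, summed main effects | about +1 | below +1 |
| Main-effect sign | +4 to +10 | +2 to +4 |
| Mean of top four cells | +6 to +15 | +3 to +6 |
| Best single cell | +10 to +22 | +4 to +8.5 |

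**5. Is it a bound?** Assume base 15% and one, two or four components each truly adding 8 points. At 15 per cell, the excess over the selected package's true effect is about 7–8, 6–7 and 4–5 points (sign) and 11–12 (top four). At 15–19 per cell the estimate falls below that true effect in about 14–45% of trials (sign), 13–16% (top four) and 5–11% (best cell, depending on how ties are broken). For z>1.96 it falls below in 14–21% if the raw cell contrast is reported, but at most about 0.1% if main effects are summed.

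**6. Can Aim 1's model supply the estimate?** One intercept + 4 main effects + 6 two-way + 4 three-way + 1 four-way = 16 parameters for 16 cells. Without covariates that model is saturated: its predicted differences from all-off are the raw cell differences. A reduced model is needed to borrow strength across cells.

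**7. Does a bootstrap that repeats selection help?** Tested with a main-effects logistic model, sign selection and unequal cells at N=240. Null, base 5, 20 and 50%: uncorrected +6.0, +9.3, +10.2; corrected +0.6, +2.4, +3.4. One, two or four active components: uncorrected 15.5, 21.6, 32.8; corrected 9.2, 15.8, 28.1; true 7.6, 14.9, 29.3.

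**The case against.** The plan is more guarded than this may suggest. The upper-limit label itself signals optimism, and under best-cell selection the figure does exceed the truth in roughly nine trials in ten or more. The contrast is additional to the full-sample factorial model. The update concedes inadequate power and mentions ranges, and a later RCT would test the package without this bias. Aim 1 speaks of testing effects, and a strict test-based rule would leave only about one point of null optimism. On cell size, 300 is the target, allocation is monitored, and the shortfall counts rest on assumed blocks and strata. Under the effect coding named in Aim 2, interaction coefficients are as precise as main-effect coefficients, so the 20-point half-width belongs to the difference-of-differences scale only.

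All of that stands as mitigation. It does not supply a rule, or an interval for this contrast; ranges promised in general are not tied to it and would not by themselves allow for selection. The RCT still inherits the choice of package and its apparent effect. Monitoring allocation is not a guarantee of balance, and the N=240 arithmetic needs no assumption about blocks: 15 is the mean.

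**Conclusion.** The cell-size sentence is wrong as written at N=240 and often true at N=300. The package contrast is neither a confidence limit nor a guaranteed bound. Its null optimism at 15–19 per cell runs from about 1 to 22 points according to a rule the plan does not state. The 8-point increment in Power and Sample Size was set per component, so it is only context for a package effect.

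A reader might infer more than the documents support:

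- That the upper limit fails under every selection rule. It does not: z>1.96 with summed main effects almost never fell below the truth.
- That +22 points is the expected bias. That is the best-cell reading, and Goals/Aims speaks of components.
- That cells must also fall short at N=300. That depends on block size and number of clinics.
- That Aim 1's factorial tests are biased. The problem is confined to the added contrast.

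The simulations assume independent binomial outcomes, additive effects in the active scenarios, two genders and blocks of 16 or 32.

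**What to change.** **July 2022 update.** Replace the per-cell guarantee with an average of 15–19 per cell, noting that individual cells may be smaller. Give a minimum only if it is computed from the actual block size. Replace the claim of stability with the half-widths above.

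**Aim 1.** Prespecify how components are selected, including how low cost enters. Estimate the package effect from a stated reduced model, for example main effects plus any retained 2-way interactions. Report it with an interval and a bootstrap that repeats the selection. Label any raw cell contrast descriptive and selection-biased, and drop the upper-limit label.

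**Cost.** Wording changes, one named model and one bootstrap; no new data. The reduced model assumes that omitted interactions are small, which matters in a study looking for combinations. The bootstrap removes only part of the optimism, was about 1 point low with four active components, and was tested only under sign selection with a main-effects model. Its nominal 95% interval covered as little as 85%, with total width 21–38 points at N=240. The reported effect will look smaller.
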